Healthy Hydration Pilot in Elementary Schools

NCT06132763

05/07/2025

1. STUDY DESIGN AND METHODS. Our team recognizes the broader context that influences student hydration behavior. As such, the proposed research involves multiple components aligning with levels of the social-ecological framework to advance water equity. All schools in will have hydration stations and be operating under their model hydration policy in the 2022-23 school year. We will randomly select a pair of matched elementary schools for study inclusion. One school will serve as the Intervention school and the other as the Control. To test study aims, we will conduct a 2 (Intervention and Control) x 2 (baseline and post) cluster pilot RCT, with students nested within schools. Both schools will receive water bottles and Hydration Tip sheets. In the Intervention school, we will collaborate with student ambassadors and our Community Advisory Board (CAB) to develop hydration marketing materials. We will then pilot a 12-week intervention that includes a student-developed marketing campaign plus positive reinforcement of water bottle use in school. Teachers will receive state standards of learning-aligned lessons related to hydration. Assessments of hydration station usage will be conducted at baseline, weekly throughout the intervention, and 12-weeks (post). Beverage selection and water bottle use at lunch will be assessed at baseline, monthly throughout the intervention, and post. School personnel and 4th and 5th grade students will complete online surveys via REDCap at baseline and post. The primary aim is to determine intervention feasibility, evidenced by the ability to recruit and retain student ambassadors, implement the intervention components as planned, and ratings of school personnel satisfaction. Secondary outcomes of interest are 1) % of students with water bottles at lunch, 2) hydration station usage, and 3) sugar-sweetened beverage (SSB) selection at lunch. We will also test our protocols for assessing body mass index (BMI) and dental caries status with a subset of 3rd grade students. Although we do not anticipate change on these measures in this short duration, these will inform methods applied in a larger trial. To acknowledge the district's time and involvement in this study, each participating school will select an incentive valued up to \$500 that is related to an identified school need (e.g., kitchen, recess, or PE equipment).

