1.1 Target Population and Setting. The respective school district serves >26,000 students within 25 elementary schools (22 Title I and thus eligible for this study). Students identify as Black (56%), white (21%), Latinx (19%), multiracial (3%), and Asian (2%). The majority (>90%) of students participate in the NSLP and all students receive free meals. For the current study, all Title I elementary schools will first be categorized based on race (%Black) and ethnicity (%Hispanic); two matched schools will be randomly selected and assigned to either Intervention or Control group (methods successfully applied in our prior work in this district). Potentially eligible schools have a mean enrollment of 400 students (range 145-854); we anticipate obtaining lunchroom observations from >80% of students on each rating day, for a projected sample of ~320 student observations per day in each school. Numbers will change based on the population of the selected schools. A subset of 3rd graders who have active parent consent and student assent will complete biomedical assessments.

1.2. Student Ambassadors. We will work with a local non-profit that has successful health-related programming in the schools and the school district to solicit student ambassador nominations. Both student self- and teacher nominations will be accepted. Teachers will describe ambassador roles and responsibilities, which include determining incentives, developing marketing materials and assisting the teacher ambassador with recording hydration station usage from the device, and other intervention-related tasks as relevant. Interested students will complete an interest form, signed by their parent/guardian. Teachers will select 2-3 ambassadors. In these ways, this study will build capacity and partner with students, teachers, and the CAB to enhance study relevance. To maintain study rigor, we will train students and teacher liaisons on study procedures. Ambassadors will receive compensation for this work.

1.3. Marketing Design. In the Intervention school, student ambassadors and a graphic design consultant will attend 5 meetings to develop healthy hydration promotional materials. Meetings will be guided by Appreciative Inquiry (AI) an asset-based approach to engage participants in

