Healthy Hydration Pilot in Elementary Schools

NCT06132763

05/07/2025

D. POWER/ANALYSIS PLAN. Students, the unit of analysis, are nested within schools. Thus, we have a cluster RCT with 2 clusters (intervention and control school). To detect a 10% mean difference in water bottle usage between groups, with a common SD of 15, an unadjusted sample size of 17/group would be needed. Adjustments to this sample size were made using a variance inflation factor (based on the assumption of an ICC of .03) to accommodate homogeneity within the clusters. Using this assumption, 2 clusters of average size of 200 is sufficient to detect the hypothesized difference at $\alpha=.05$ (two-sided) and a desired power of 80%. Thus, our proposed sample will be more than adequate to evaluate study aims. Contingency tables and frequency distributions will be evaluated and descriptive and inferential statistical analysis applied. Differences between schools in % of students with water bottles, hydration station counts (per student), % of students with SSBs at lunch, and beverage intake (BEV-Q; SSB, water, milk) will be evaluated using chi-square analysis. Difference between baseline and post values on these study outcomes will indicate an intervention effect, with one-way ANOVA conducted to test group differences. We will also graphically examine monthly trends in hydration station usage by school. Paired t-tests will examine differences in these outcomes by school. We will also examine interrater reliabilities (Kappas) among dental assessors and report baseline and post body mass index (BMI, BMIz, BMI percentile) and dental caries status (ICDAS criteria), as well as any observed differences by school over time (although none are expected in this study duration) to inform methods applied in a future trial. Descriptive statistics will be applied to examine trial feasibility (e.g., recruitment, retention, satisfaction, and implementation). Triangulating all data sources will be the basis for deriving final conclusions and recommendations for our future intervention.

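### The SAP calls the sample more than adequate for the study aims after sizing only a secondary outcome; the primary feasibility aim has no sample size justification and no pre-specified success or failure result

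*SAP*

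**What the plan says.** Protocol section 1 states the primary aim and its first two indicators: "The primary aim is to determine intervention feasibility, evidenced by the ability to recruit and retain student ambassadors, implement the intervention components as planned". A third indicator, how satisfied school staff say they are, completes the list. The protocol then ranks the other measures: "Secondary outcomes of interest are 1) % of students with water bottles at lunch, 2) hydration station usage". The choice of sugary drinks is the third of these.

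On ambassadors, Protocol section 1.2 says: "Teachers will select 2-3 ambassadors". Section 1.3 places their work in one arm: "In the Intervention school, student ambassadors and a graphic design consultant will attend 5 meetings to develop healthy hydration promotional materials".

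SAP section D has one sample size calculation, for water bottle usage. It takes a difference of 10, a common SD of 15, two-sided alpha of .05, 80% power and an ICC of .03. It arrives at 17 per group unadjusted and then at two schools averaging 200 students. The conclusion follows directly: "Thus, our proposed sample will be more than adequate to evaluate study aims".

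For feasibility, the SAP plans descriptive summaries only, and it closes with: "Triangulating all data sources will be the basis for deriving final conclusions and recommendations for our future intervention". Neither document gives a recruitment or retention target, a delivery threshold, a satisfaction cut-off or a progression rule.

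**The concern.** The adequacy statement covers the study aims, and the first of these is feasibility. The calculation behind it concerns an outcome that the protocol ranks as secondary, so the claim is unsupported for the primary aim.

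The pilot exists to inform a larger trial. With no result tied to a decision in advance, any cut-off for feasible or not feasible would be chosen after the data are known. A reader of the final report could not tell whether the feasibility conclusion met a standard or whether the standard was fitted to the results. The adequacy sentence makes this worse, because it suggests that the question of sample size for the primary aim has been settled.

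**Working it through.** **1. Which aim was sized?** Set side by side, Protocol section 1 puts feasibility first and water bottles second, while SAP section D sizes water bottles and nothing else.

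**2. What exists for each feasibility indicator?**

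| Indicator | Planned quantity in the documents | Success or failure value |
|---|---|---|
| Ambassador recruitment and retention | 2-3 students (1.2); Intervention school wherever an arm is named (1, 1.3) | None |
| Implementation as planned | 5 design meetings (1.3); weekly water-meter update and one reinforcement day per week over 12 weeks, so 12 of each; trivia and lessons, no number given (1.5.2) | None |
| Personnel satisfaction | Online surveys at baseline and post (1); number of personnel not stated | None |

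**3. How much can the ambassador count show?** If all *n* stay, the exact 95% lower limit for retention is 0.025^(1/*n*).
- *n* = 3: 0.025^(1/3) = 0.29, so 29% to 100%.
- *n* = 2: 0.025^(1/2) = 0.16, so 16% to 100%.

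The SAP plans no such interval. These figures only show that retention is a count to report and cannot serve as an estimate.

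**4. Does the statement hold for the outcome that was sized?** All inputs are from SAP section D, except the 320 daily observations per school, which come from Protocol section 1.1.

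First, the SAP's figure of 17 per group. For two independent groups, *n* = 2 × [SD × (1.960 + 0.842) / difference]² = 2 × (15 × 2.802 / 10)² = 2 × 17.66 = 35.3, so 36 per group. The 17 is not reproduced. A one-sided test gives 28. Without the factor of 2, as for a one-sample or paired comparison, the result is 17.66. That is close to 17 (18 when rounded up), but it does not fit a comparison between groups.

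Next, the inflation for clustering, with design effect DE = 1 + (*m* − 1) × 0.03 and effective size *m*/DE per arm. Power is Φ(10 / [15 × √(2/*n*_eff)] − 1.960).

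| Students per school | DE | Effective *n* per arm | Power |
|---|---|---|---|
| 200 | 6.97 | 28.7 | 71% |
| 320 | 10.57 | 30.3 | 74% |
| No limit | – | 1/0.03 = 33.3 | 78% |

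The SAP's conclusion that 200 suffices follows from its starting figure: 17 × 6.97 = 118.5, below 200. Starting from 36, 36 × 6.97 = 250.9, above 200. With one school per arm, the effective size cannot exceed 33.3, which is below 36, so no school size reaches 80%.

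**The case against.** The strongest reply is that this is a pilot. A pilot need not be powered for feasibility, descriptive reporting is a normal choice, and the SAP plans no inference on retention, so intervals on 2-3 selected students measure an estimate nobody intended to make. That is right. The intervals carry little weight, and the absence of power for feasibility is no fault in itself. What stands is that the SAP claims an adequacy it never assessed for the primary aim, and that no criterion is fixed.

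Three stronger readings are tempting, and the documents do not support them.

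- A reader might infer that the primary aim rests on 2-3 ambassadors. They are one of three indicators; implementation and personnel satisfaction draw on other data.
- A reader might infer that the plan cannot return a finding of not feasible. The plan has countable content, so failed delivery would be visible and the investigators could call it by judgement. What is missing is a result specified in advance.
- A reader might infer from the triangulation sentence that a favourable water bottle result may stand in for feasibility. The SAP gives feasibility its own descriptive sentence and nowhere says that outcome tests decide it. It also does not say that they are kept out.

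**Conclusion.** The concern holds in this form: the adequacy statement derives only from a secondary outcome, and the primary feasibility aim has neither a sample size justification nor a pre-specified success or failure result for any of its three indicators.

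The statement is also wrong for water bottles on the SAP's own inputs: 36 per group instead of 17, and power of about 71% at 200 per school and 74% at 320, with a ceiling near 78%. These power figures assume a normal approximation, equal school sizes and an ICC of .03 treated as known. They are generous, because with one school per arm the data cannot separate the intervention from a school effect.

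The ambassador remarks assume that 2-3 is the total, all in the Intervention school. Section 1.2 names no arm, but sections 1 and 1.3 do.

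**What to change.** 1. **Delete the adequacy sentence** and state that the sample was not sized for the primary feasibility aim. Do not keep the claim in a form limited to water bottles, since the SAP's inputs do not reach the stated power there either.
2. **Set go, revise and stop criteria for progression to the larger trial**, with values chosen by the sponsor, covering all three indicators:
   - ambassadors recruited, and ambassadors still active at week 12, both as counts;
   - planned components delivered: 5 meetings, 12 weekly meter updates, 12 weekly reinforcement days, trivia and lessons;
   - the proportion of responding personnel who are satisfied, with the number responding.

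   Treat these as delivery counts and not as precise estimates. Five meetings with 2-3 ambassadors give 10-15 attendances, but these are repeated observations on the same students. The meetings also come before the 12-week pilot, so attendance cannot replace retention at week 12.
3. **State that the feasibility conclusion rests on these criteria** and that secondary-outcome tests are reported separately.
4. **Be open about timing.** Protocol section 1.5.1 plans the kick-off for January 2023, and both documents are dated 05/07/2025. If post data have already been seen, label the criteria post hoc; the adequacy sentence should be removed in either case.

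The cost is SAP wording and simple delivery logs, which the documents do not describe and which may have to be set up or reconstructed. The downside for the sponsor is that the pilot can then return a revise or stop result.

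### The SAP assigns chi-square to hydration station counts and BEV-Q intake, and with one station total per school per time point its ANOVA and paired t-tests have no error degrees of freedom

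*SAP*

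**What the plan says.** Section D of the SAP lists four outcomes in one sentence and assigns them all to one test. Two are percentages of students (water bottles, and SSBs at lunch). The other two are "hydration station counts (per student") and BEV-Q intake: "beverage intake (BEV-Q; SSB, water, milk) will be evaluated using chi-square analysis". The next sentence moves to change: "Difference between baseline and post values on these study outcomes will indicate an intervention effect, with one-way ANOVA conducted to test group differences". Later: "Paired t-tests will examine differences in these outcomes by school". Between these, the SAP plans a display: "We will also graphically examine monthly trends in hydration station usage by school".

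On the design, the SAP states: "Thus, we have a cluster RCT with 2 clusters (intervention and control school"). On data capture, Protocol section 1.2 has ambassadors help with "recording hydration station usage from the device". Section 1.5.2 describes a display of the school's weekly refills, and section 1 schedules usage assessments at baseline, each week and at 12 weeks. No document describes a refill being attributed to an individual student, and none gives categories or scoring for the BEV-Q.

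**The concern.** Chi-square suits the two percentages. It does not obviously suit a refill count or an amount of beverage consumed, and the SAP's own ANOVA and t-tests treat those same two outcomes as numeric. For station usage there is a further difficulty: if the device yields one total per school, there may be nothing from which to estimate error.

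Station usage is one of the three secondary outcomes named in Protocol section 1, and the SAP says that change in these outcomes will indicate an intervention effect. An analyst following the plan literally would get no ANOVA or t-test result for station usage. The analyst might then fall back on a chi-square whose error rate is not controlled, or choose replicates that the plan does not define. For BEV-Q, two analysts could follow the plan and treat the same responses differently.

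**Working it through.** The plan gives no figure for this point. Its sample size calculation concerns water bottle usage and does not enter here.

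**1. Level of the station data.** The SAP calls the outcome a count per student. The Protocol describes a device reading and a weekly school number of refills. The most plausible reading is a school total divided by enrollment. This is an inference.

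**2. Degrees of freedom with one baseline and one post total per school.**
- One-way ANOVA on change: 2 change values, 2 groups, so error df = 2 − 2 = 0.
- Paired t-test within a school: 1 pair, so df = 1 − 1 = 0.

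Run in software, both return no statistic and no p-value.

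**3. Chi-square on two refill totals.** For totals x and y from schools of equal size, the test is equivalent to z = (x − y)/√(x + y). The denominator is right only if each total is Poisson, that is, if refills are independent events. If the variance of each total is v times its mean, z has variance v when there is no true difference, so

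type I error = 2 × [1 − Φ(1.96/√v)].

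| v (assumed) | 1.96/√v | type I error |
|---|---|---|
| 1 | 1.960 | 5.0% |
| 2 | 1.386 | 16.6% |
| 3 | 1.132 | 25.8% |
| 5 | 0.877 | 38.1% |

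The documents give no value for v. A ratio above 1 is plausible because the same students refill repeatedly and some refill far more often than others.

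**4. Weekly readings or several devices as replicates.** The ANOVA and t-tests can then be computed. All replicates in an arm still come from the same school, so any school-specific change over the 12 weeks is indistinguishable from an intervention effect. The documents do not say how many readings form the baseline, how many devices there are, or what the t-test pairs.

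**5. BEV-Q.** Set side by side, the between-school contrast uses a test for categories, while the change contrasts use tests for means. No categories are stated that would support the former, and no score is stated that would support the latter. No loss can be quantified without the scoring.

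**The case against.** Four objections deserve an answer.

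*Station data may be student-level.* The SAP names students as the unit of analysis and says per student, and the weekly refill display in the Protocol falls under an Intervention-school heading, so capture in the Control school is not described there. This stands as a limit. If refills were recorded by student, the 0 df result would not apply. Chi-square would still need categories that the SAP does not define, and there would still be one school per arm.

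*Larger error rates.* A reader might apply the SAP's design assumption ("based on the assumption of an ICC of .03") to the station totals. At the mean enrollment of 400, the variance ratio is 1 + 399 × .03 = 12.97, which gives a chi-square type I error of 59%. The documents do not support this as the error rate of the intervention claim. The SAP uses chi-square for differences between schools and bases the intervention effect on change. A school difference that persists from baseline to post cancels in change: in a simulation of Poisson refills (assumed mean 2 per student), a test on change rejected about 5% of the time. The ICC is also stated for water bottle usage, not refills. Nor does repeat refilling contradict it, since repeat refilling is dependence within a student and the ICC describes similarity within a school.

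*An error rate for weekly replicates.* A reader might also want one. It depends wholly on how the analysis is built. With independent readings and no school difference, subtracting one shared baseline reading from 12 weekly readings gives 57% for the ANOVA; pairing 12 baseline with 12 later readings gives about 5%. The SAP specifies neither, so neither figure belongs to the plan.

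*It is a pilot.* The primary aim is feasibility, analysed descriptively, and conclusions are to draw on all data sources together. That limits the consequence, and it also supports descriptive reporting of station usage.

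Clustering in the two lunch percentages is a separate matter. Chi-square fits their data type.

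**Conclusion.** The concern holds for two outcomes. For station usage, on the reading that the device gives one school total per time point, the planned ANOVA and paired t-tests are undefined (0 error df). The planned chi-square has a type I error of 17% to 38% at a nominal 5% if the variance-to-mean ratio is 2 to 5. The first result rests on the inferred level of the data, the second on an assumed ratio. Replicates would make the tests computable without making them informative about the intervention.

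For BEV-Q, the tests are inconsistent with each other and the scoring is unstated. Whether chi-square is wrong for it cannot be settled: if responses are categories, it could be suitable. The documents also do not show when the scoring was fixed, so a reader should not infer that it was left until after the data were seen.

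The SAP should be changed, but the reach is limited. The primary feasibility aim is untouched, and BEV-Q is not among the three named secondary outcomes.

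**What to change.** **Station usage.** Drop chi-square, ANOVA and paired t-tests. State how many readings and devices form each time point. Extend the planned monthly graph to weekly refills per enrolled student in each school. Report the baseline and post rates, and (post/baseline) in the Intervention school divided by (post/baseline) in the Control school, without a p-value.

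**BEV-Q.** Fix the scoring before analysis and use one method matched to it for both the between-school and the change contrasts. If the score is numeric, replace chi-square with the school difference in mean change, as the single stated estimand. Describe any interval as reflecting variation between students only.

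**Interpretation.** State that with one school per arm, all between-school comparisons are descriptive and do not separate the intervention effect from school differences.

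**Cost.** Some SAP rewording and simple summaries of data already planned, with no new data collection. The downside is that station usage will have no p-value.

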1.5. Hydration Intervention. (Intervention school)

1.5.1. Hydration Kick-Off. In January 2023, the study team, in collaboration with teachers and community organizations, will host a kick-off event at the Intervention school. All pre-K through 5th grade students and teachers will receive clear refillable water bottles with carabiners (so students can attach the water bottle to their backpack, a lesson learned in our prior work), a Hydration Tip sheet, and verbal and written guidance to bring their water bottle to school daily for use at the hydration station. Students will select a decal for their water bottle and their name will be written on the bottle, a strategy to increase ownership and help if it is misplaced.

Hydration Tip Sheets and intervention information will be sent home to parents via established district parent communication strategies (in English and Spanish). Water bottles will stay at school with cleaning materials and instructions provided for each classroom.

1.5.2. Hydration Intervention. Students will be informed at Kick-off that they could receive prizes if they use their water bottle in school. We will conduct a 12-week intervention that includes: 1) a marketing campaign with student-developed materials, 2) use of incentives (determined by student ambassadors) to positively reinforce water bottle use, 3) hydration trivia, 4) hydration lessons. Marketing materials will be placed strategically in high traffic areas including hallways, school entries/exits, the lunchroom, and on floor decals and walls near hydration stations. A **Hydration Headquarters** will be set up in the school displaying a "water meter" illustrating the increasing number of water bottle refills from their school's hydration station each week (colored in weekly by student ambassadors). This CAB-generated strategy is designed to create group cohesion towards a common healthy goal and enhance student motivation. Study personnel positively reinforce water or water bottles observed in the lunchroom 1 day/week throughout the 12 week intervention. Teachers receive classroom water procedure signs with space to personalize details regarding when students can fill, store, and clean their water bottles. Laminated hydration tips will be posted in each classroom. Teachers will receive hydration lessons by subject matter and grade that align with SOL's.

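### Paired t-tests and change-score ANOVA are planned for lunchroom bottle and SSB ratings, but no link between a student's baseline and post ratings is described

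*SAP*

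**What the plan says.** SAP section D sets the unit of analysis: "Students, the unit of analysis, are nested within schools". It then lists the outcomes: "Differences between schools in % of students with water bottles, hydration station counts (per student), % of students with SSBs at lunch", followed by self-reported beverage intake from the BEV-Q. Chi-square is named for differences between schools. For change over time it says: "Difference between baseline and post values on these study outcomes will indicate an intervention effect, with one-way ANOVA conducted to test group differences". After a sentence on graphing monthly station usage, it adds: "Paired t-tests will examine differences in these outcomes by school".

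The protocol describes the lunch data in two places. Section 1 gives the timing: "Beverage selection and water bottle use at lunch will be assessed at baseline, monthly throughout the intervention, and post". Section 1.1 gives the coverage: "we anticipate obtaining lunchroom observations from >80% of students on each rating day". The same sentence then turns this coverage into an expected daily number: "for a projected sample of ~320 student observations per day in each school". Section 1.4 provides for opt-out notification, with active consent and assent only for the 3rd-grade biomedical measures. Section 1.2 has ambassadors help to record station usage from the device. No section describes a roster, a study ID or any matching of one child's ratings across days.

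**The concern.** A paired t-test, or an ANOVA on individual change with the student as unit, needs the same child's value at baseline and at post. The lunch data as described are a set of observations on one day and another set on a later day. The children in the two sets overlap to an unknown extent, and nothing says which record belongs to whom.

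Bottle use and SSB selection at lunch are two of the three secondary outcomes in protocol section 1. The third, station usage, is a device reading and so has no student-level pair. An analyst following the SAP would have to devise a pairing or depart from the plan with no stated rule. The pilot is meant to inform a future trial, so the method should be one that its data can support.

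**Working it through.** **The plan's own figure.** Mean enrolment is 400 and coverage is taken as 80% (both protocol 1.1): 0.80 × 400 = 320. The projected daily number reproduces.

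**What two daily percentages determine.** Let p1 and p2 be the proportions with a bottle at baseline and post, d = p2 − p1, and n the number of students. Let L be the share who had a bottle at baseline but not at post. The share who change in either direction (the discordance) is D = 2L + d. For a binary rating:

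- Paired: SE = √[(D − d²)/(n − 1)] and t = d/SE.
- Unpaired: SE = √[(p1(1 − p1) + p2(1 − p2))/n] and z = d/SE.

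The unpaired SE uses only p1, p2 and n. The paired SE needs D, and so L, which can be known only by following each child. For a rise, L can lie anywhere from 0 to the smaller of p1 and 1 − p2.

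**Numbers put in.** The documents give no expected rates, so these are assumptions, with n = 320 in one school and the same 320 children on both days.

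For 30% to 40%, L runs from 0 to 0.30, so D runs from 0.10 to 0.70.

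- D = 0.10: SE = √(0.09/319) = 0.0168, t = 5.95
- D = 0.70: SE = √(0.69/319) = 0.0465, t = 2.15
- Unpaired: SE = √[(0.21 + 0.24)/320] = 0.0375, z = 2.67

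| Assumed change | Range of D | Paired t (p) at lowest D | Paired t (p) at highest D | Unpaired z |
|---|---|---|---|---|
| 30% to 40% | 0.10 to 0.70 | 5.95 (<0.0001) | 2.15 (0.032) | 2.67 |
| 50% to 60% | 0.10 to 0.90 | 5.95 (<0.0001) | 1.89 (0.059) | 2.56 |
| 30% to 35% | 0.05 to 0.65 | 4.10 (0.00005) | 1.11 (0.27) | 1.35 |

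The last unpaired value is 0.05/√[(0.21 + 0.2275)/320] = 0.05/0.0370 = 1.35. In the second and third rows the data as described do not even settle on which side of 0.05 the paired result falls.

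**How many pairs there would be.** With 80% of 400 seen on each of two days, the number seen on both is:

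- at least 320 + 320 − 400 = 240, a loss of 80/320 = 25% of each day's observations;
- 0.80 × 0.80 × 400 = 256 if absences are independent, a loss of 64/320 = 20%;
- at most 320, with no loss.

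These losses arise only if ratings are linked and the paired test drops children seen once. With 240 pairs and the same 30% and 40% among them, the paired t would run from 5.15 to 1.86.

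**Reading the pairing at school level.** If each school's percentage is the unit, each school supplies one baseline-post pair. That leaves n − 1 = 0 degrees of freedom and no variance estimate.

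**The case against.** The strongest reply is that silence is not proof. The available protocol stops at section 1.5.2 and contains no lunchroom rating procedure, and nothing says the ratings are anonymous. Honouring opt-outs may require raters to recognise individual children. This stands. A reader might infer that the paired test cannot be run at all, but the documents support that only for the data as described, not for the data as collected.

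A reader might also look to the bottle as a link, since at the Intervention school's kick-off "their name will be written on the bottle". Section 1.5.1 gives the purpose as ownership and recovery of lost bottles. Nothing proposes linking records by it, so no bias from such linkage should be charged to the plan.

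The SAP may have had aggregated values in mind. The outcomes are written as percentages, and the SD of 15 in the sample-size statement does not look like a yes/no rating, whose SD is √(0.30 × 0.70) = 46 points at 30% and 50 points at 50%. That is a genuine ambiguity. But the SAP names students as the unit, and the school-level reading leaves no variance for a within-school paired test.

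The sentence on paired tests directly follows one on station usage, so its antecedent is loose. Reading it as station usage alone does not help, because a device count has no student pair.

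Finally, the primary aim is feasibility, analysed descriptively, and with one school per arm even a sound paired test would not isolate an intervention effect. This limits the consequence without making the stated test fit the data.

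**Conclusion.** The point holds for the data as described. Student-level paired and change-score tests are planned for lunch outcomes that the protocol presents as repeated cross-sections, and for station counts that have no student-level pair. It would be wrong to infer that change over time is lost: the net change in each school's percentage can be obtained from all students observed. What cannot be obtained without linkage is the within-student change and its standard error.

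The size is shown by the paired t of 5.95 to 2.15 from the same 30% and 40%. It rests on assumed rates, 320 students and complete overlap. The 0 to 25% loss of observations is conditional on linked ratings, coverage of exactly 80% and enrolment of 400; the protocol expects coverage above 80%, which would make the worst case smaller. No bias in any estimate has been shown. This should be corrected before analysis, but it concerns secondary outcomes of a feasibility pilot.

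**What to change.** In SAP section D, for bottle use and SSB selection at lunch, replace the paired t-tests and the change-score ANOVA with wording such as:

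*For each school and rating day, we will report the percentage of observed students with a water bottle and with an SSB, using all students observed that day. For each school we will report the baseline-to-post difference in percentages with an unpaired 95% confidence interval, and then the difference between schools in those changes. These results are descriptive because there is one school per arm.*

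For the assumed 30% to 40%, the within-school interval would be 10 ± 1.96 × 3.75, or 2.65 to 17.35 percentage points.

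Report station counts per enrolled student descriptively by week. Keep paired analysis only for records linked by student ID: the 4th and 5th grade surveys if they are linked, and the consented 3rd-grade measures.

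If lunch ratings are in fact linked, state the identifier and use a paired method for binary data: McNemar's test, or a mixed model that keeps children seen on only one day.

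The cost is SAP wording, with no new data. The small downside is that any precision gained from within-student correlation is given up. If a child's ratings on the two days are positively correlated, the unpaired interval will be somewhat too wide.
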